Role of Hepatic Glycogen on Nocturnal EGP IN T2D

Unique Protocol ID: 22074

Secondary ID: R01DK029953

ClinicalTrials.gov ID: NCT04416204

Protocol:

15 ND and 14 T2D subjects will be studied on two occasions (*glycogen loading vs. no glycogen loading*). Human Subjects: All studies and protocols will be approved by the UVA Institutional Review Board. These studies will be conducted in 15 T2D and 15 ND subjects (age 30 - 80 years, BMI 20 - 35 kg/m²) matched for age and degree of obesity. Menstruating female subjects will be studied during the follicular phase of their menstrual cycles. Screen visit: Subjects will report to the UVA CRU after an overnight fast in the morning. After obtaining informed consent, a history and physical examination will be performed. Blood will be collected for complete blood count, serum creatinine, electrolytes, lipids, and HbA1c. A standard urinalysis will be performed. All women of childbearing potential will have a negative pregnancy test within 24 hours of the study visit. A dietary history will be taken at the time of screening to ensure adherence to a weight maintaining diet consisting of ~ 200 grams of carbohydrates per day and their diets met ADA guidelines for protein, fat, and carbohydrates. They will be instructed to adhere to the diet between screen and study visits. Body composition may be measured using measuring scale. Enrolled T2D subjects will withdraw oral hypoglycemic agents 2 weeks prior to study visit (medications will resume after each study visit) and will monitor their fingerstick glucoses. If three successive fingerstick glucose values ≥ 300 mg/dl, then they will resume their medication/s and will be withdrawn from study. Physical activity will be assessed with the Paffenbarger activity questionnaire and activity monitored by the subject with a Fitbit. Subjects will refrain from unusual / unaccustomed physical activity and should not change their body weight by $>2\%$ between screen and study visits. Pre-study visit protocols: All subjects will participate in both protocols outlined below in random order prior to their study visits. The study visits will be separated by 3-6 weeks *to allow for elimination of deuterated water* and will be identical except for the preceding glycogen loading or no glycogen loading protocols.

Glycogen loading (GL) protocol: Subjects will consume an isocaloric diet [60% carbs, 20% protein, 20% fat (33 kcal/kg/day)] prepared by the research dietician of the UVA CRU for 3 days prior to the overnight study 1. During this period, subjects will limit their daily activity to normal walking that will be monitored with Fitbit. Unusual physical activity will be discouraged.

No glycogen loading (NGL) protocol: Subjects will consume an isocaloric diet [40% carbs, 20% protein, 40% fat (33 kcal/kg/day)] prepared by the research dietician of the UVA CRU for 3 days prior to the overnight study 2. During this period, subjects will do their normal walking (monitored by Fitbit) but unusual physical activity will be discouraged.

Sample size estimation: The experimental design was configured with parallel cohorts (ND and T2D) with primary hypotheses of within cohort comparisons (i.e., glycogen loaded (GL) vs. non-glycogen loaded (NGL) meals). For sample size planning purposes, a paired t-test was utilized. At time of study design, no preliminary data existed on the effect of post prandial glucose uptake, so the effect size observed was utilizing a similar overnight study estimating GNG 3. For the studied T2D participants, the mean (SD) GNG ($\mu\text{mol/Kg/min}$) rate at 0700 hrs. was 12.9 (2.8) and 10.6 (3.0) under test and control conditions. This resulted in a change of 2.05 (1.68) between the two conditions. Assuming a similar magnitude of change of 2 units is clinically relevant

and a SD of the difference of 1.75 (to be conservative), a sample size of 9 was required to achieve 80% power at the $\alpha=0.05$ level of significance. The protocol was written to study up to 15 participants per cohort to provide additional precision in the estimates and address the uncertainty in the glycogen loading effect. *Primary analysis.* A linear mixed model with compound symmetry variance structure was fit to the data that had repeated measurements at 0100, 0400 and 0700 hrs. This model specified parameters for study group (T2D vs. ND), time of night (0100, 0400 and 0700 hrs) and the glycogen loading treatment (GL vs NGL). This model estimated 12 ($2 * 3 * 2$) individual means for each outcome measure, with GNG planned as the primary endpoint at time of study planning. In order to summarize the effects of the model, model-based means were constructed to provide pooled estimates of the differences in means of interest. In some cases, several of the model-based means were averaged together (e.g., a “diabetes” effect was obtained by comparing the mean of the 0100, 0400 and 0700 hrs measures under both GL and NGL values averaged for each patient group). All p-values are unadjusted and reported in conjunction with estimates and 95% confidence intervals. Statistical analysis was performed using R version 4.1.2.

Reference

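### The primary GL vs NGL contrasts are within cohort, but their intervals come from one compound-symmetry model over T2D and ND with no stated cohort variance or visit term; a paired analysis per cohort is a cheap safeguard.

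*Combined protocol and SAP*

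**What the plan says.** Under Sample size estimation: "The experimental design was configured with parallel cohorts (ND and T2D) with primary hypotheses of within cohort comparisons", that is, GL against NGL in ND and again in T2D. The same paragraph adds: "For sample size planning purposes, a paired t-test was utilized". The planning SD of the paired difference, 1.75, is rounded up from a T2D result: "This resulted in a change of 2.05 (1.68) between the two conditions". No SD for ND is given anywhere.

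The Primary analysis paragraph reads: "A linear mixed model with compound symmetry variance structure was fit to the data that had repeated measurements at 0100, 0400 and 0700 hrs". On the mean structure: "This model specified parameters for study group (T2D vs. ND), time of night (0100, 0400 and 0700 hrs) and the glycogen loading treatment". The model has 12 means (2 groups × 3 times × 2 treatments), so both cohorts sit in one fit. Results are estimates with 95% confidence intervals and unadjusted p-values.

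On the design, the opening Protocol line has "15 ND and 14 T2D subjects will be studied on two occasions", in random order, and Pre-study visit protocols has "The study visits will be separated by 3-6 weeks".

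The text does not say whether the compound-symmetry block is a subject's six readings or the three readings of one night. It does not say whether variances may differ by cohort, or which contrast (0700 hrs or an average over the night) is the primary within-cohort comparison.

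**The concern.** A paired t-test takes its standard error from one cohort's own GL minus NGL differences. A joint compound-symmetry model, read in the ordinary way, takes it from one residual variance shared by T2D and ND. Two consequences follow.

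- If within-subject variance differs between cohorts, the noisier cohort's interval is too narrow and the other's too wide. The direction in this trial is unknown.
- If the block is all six readings, readings three hours apart on one night are treated as no more alike than readings from visits weeks apart after different diets. If same-night readings do share variation, the residual variance is too small for a between-visit contrast, and intervals are too narrow in both cohorts. Giving each cohort its own residual variance does not repair this.

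Each primary result is an interval and a p-value, so the standard error carries the conclusion.

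**Working it through.** **The plan's own figure.** Inputs from Sample size estimation: change 2, SD of difference 1.75, α = 0.05 (two-sided assumed), 80% power. Exact paired t-test power uses the noncentral t with noncentrality (2/1.75)√n on n − 1 df. n = 8 gives 79.1% and n = 9 gives 85.0%, so the stated 9 reproduces. At n = 14 power is 97.6%, and at n = 15 it is 98.4%.

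**Set-up for the check.** 14 T2D and 15 ND subjects, two visits, three times, complete data, no period effect. Each reading is a cell mean + subject effect + visit-within-subject effect + residual. Let σ² be the within-subject variance (visit plus residual) and p the share of it common to one night. The SD ratio between cohorts, p and the six-reading block are assumptions, because the documents give none of them.

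**Unequal cohort variance (p = 0).** Residual df are 5 × 13 = 65 for T2D and 5 × 14 = 70 for ND, 135 in all. The pooled variance is (65σ²_T2D + 70σ²_ND)/135. With T2D noisier by 1.25, it is (65 × 1.5625 + 70)/135 = 1.271, taking ND as 1. The reported standard error is then √(1.271/1.5625) = 0.90 of the true one in T2D, and √1.271 = 1.13 times the true one in ND. Simulated 95% coverage (100,000 trials per setting, night average):

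| Noisier cohort, SD ratio | T2D | ND |
|---|---|---|
| none, 1 | 95% | 95% |
| T2D, 1.1 | 94.0% | 96.1% |
| T2D, 1.25 | 92.3% | 97.2% |
| T2D, 1.5 | 90.2% | 98.7% |
| ND, 1.1 | 96.0% | 93.9% |
| ND, 1.25 | 97.4% | 92.6% |
| ND, 1.5 | 98.8% | 90.8% |

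**Same-night sharing (equal cohort SDs, six-reading block).** Of a subject's 5 within-subject df, one is between visits, with expectation σ²(1 − p) + 3σ²p, and four are within visits, with expectation σ²(1 − p). The fitted residual variance therefore averages σ²(1 − p) + (3/5)σ²p = σ²(1 − 0.4p).

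- At 0700 hrs the true variance of the contrast is 2σ²/n and the reported one is 2σ²(1 − 0.4p)/n. The standard-error ratio is √(1 − 0.4p).
- For the night average the true variance is (2/3)σ²(1 + 2p)/n and the reported one is (2/3)σ²(1 − 0.4p)/n. The ratio is √[(1 − 0.4p)/(1 + 2p)].

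| p | SE ratio, 0700 | Coverage, 0700 | SE ratio, night average | Coverage, night average |
|---|---|---|---|---|
| 10% | 0.98 | 94.5% | 0.89 | 92% |
| 25% | 0.95 | 93.7% | 0.77 | 87% |
| 50% | 0.89 | 92% | 0.63 | 79% |

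Coverage is the same to within sampling error with one common residual variance or one per cohort.

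**Paired analysis per cohort.** On 13 and 14 df, coverage was 94.8 to 95.2% across all 28 settings (SD ratio 1 to 1.5 in both directions, p from 0 to 50%).

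**Price if the simple model is right.** Expected T2D half-width at 0700 hrs with SD 1.75, where 0.981 and 0.998 correct for the expected value of an estimated SD: paired 2.160 × 0.981 × 1.75/√14 = 0.99; joint 1.978 × 0.998 × 1.75/√14 = 0.92. The ratio is about 1.07.

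**The case against.** The strongest reply is that nothing here is shown to be wrong. The 12-mean model gives GL against NGL within each cohort directly and without bias. The code may well have contained a visit term or separate variances. With equal variances and no same-night sharing the model covers at 95%, and at an SD ratio of 1.1 it loses about one point. All of that stands.

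Three stronger readings are tempting, and the documents do not support them.

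- A reader might infer that the plan contradicts itself by promising a paired t-test and then fitting a mixed model. The paired t-test is named for sizing only, and no document names it as the analysis.
- A reader might take 79% as the coverage of the primary result. That needs half the within-subject variance to be shared within a night and a night-averaged contrast. The plan says means were averaged in some cases, and its example is the T2D against ND effect. At 0700 hrs, the time used for sizing, the same sharing gives about 92%.
- A reader might assume the block is one night and work out a large loss of pairing from the SDs in "rate at 0700 hrs. was 12.9 (2.8) and 10.6 (3.0) under test and control conditions" and the SD of change, 1.68. Such a block would lose the crossover pairing and tend to make intervals too wide. Its size cannot be taken securely from these inputs: the two means differ by 12.9 − 10.6 = 2.3, while the stated change is 2.05, so the figures may not describe the same subjects. No figure on that basis is used here.

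The paired analysis would also come after the fact, since the Primary analysis is written in the past tense, and leaving the contrast open would add analyst choice. That argues for fixing one contrast and labelling the analysis as added. The check assumed no period effect; the stated model lists no period term either, so this does not favour one method over the other.

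**Conclusion.** The concern holds as under-specification with a more robust option available from the same data. The within-cohort intervals and p-values rest on equal within-subject variance in T2D and ND and, under a six-reading block, on same-night readings being no more alike than readings from different visits. The documents neither support nor exclude either condition.

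Over the assumed ranges, the loss at 0700 hrs is modest: about 3 points in the noisier cohort at an SD ratio of 1.25, and up to about 3 points from same-night sharing alone. It becomes large only for a night-averaged contrast with substantial sharing. The actual SD ratio and share are unknown, so neither the direction nor the size of any error in this trial can be stated. It should be addressed; confidence that it matters in these data is medium.

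**What to change.** 1. Beside the existing model, and labelled as added, report for each cohort the mean GL minus NGL difference in GNG at 0700 hrs, its SD and a 95% confidence interval, on 13 df (T2D) and 14 df (ND). Give the mean of the three times as supportive.
2. Keep the joint model for T2D against ND contrasts. Add a visit-within-subject term and cohort-specific residual variance, and state what the compound-symmetry block is. If the fitted model already had these terms, one sentence saying so resolves most of the point.
3. Do not let the choice rest on a preliminary test of equal variance. On 13 and 14 df it detects an SD ratio of 1.25 about 12% of the time and 1.5 about 30%.

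The cost is a few sentences and a re-analysis of existing data. Intervals are about 7% wider if the simple model is right, and power at the planning values stays at 97.6% (n = 14) and 98.4% (n = 15). A plain paired analysis drops any subject with only one visit. A model fitted to each cohort separately, with visit nested in subject, would keep them; its simulated coverage was 95.0 to 97.3% over the same sharing range.
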